4.14 Prognostic Evaluation

Prior literature has demonstrated that individual physical exam or test findings are insufficient to preclude a good outcome. Therefore, no single finding will result in cessation of support. [7, 37, 38] A multimodal workup will be employed to predict neurologic outcome. This includes clinical examination, continuous EEG monitoring, computerized tomography, somatosensory evoked potentials, and magnetic resonance imaging. [Figure 4] The clinical examination is described in Table 4. Continuous EEG monitoring is described above.

Table 4. Clinical Examination of Comatose Post-Arrest Patients

Reflex	Method to Elicit	Potential Responses
Pupil Response	Light stimulus into each pupil for 5 seconds in a darkened room. A positive response will consist of any pupillary response to the light stimulus.	0- Absent 1- Present
Corneal Response	3 drops of sterile saline will be dropped onto the cornea from a distance of 5cm. If this does not elicit a corneal response, sterile gauze will gently be used to stimulate the cornea. Any blink response will be considered a positive response.	0- Absent 1- Present
Gag Response	A Yankauer catheter will be used to suction the posterior pharynx and tonsilar pillars. Gagging will be considered a positive response.	0- Absent 1- Present
Motor Response	Supraorbital pressure, pectoral pinch, and stimulation of the nailbeds with pressure exerted by forceps will be used to elicit a response. The best motor response will be recorded.	0- No response or myoclonus 1- Decorticate posturing 2- Decerebrate posturing or withdraw to pain 3- Localization 4- Following commands

Figure 4. Timeline and testing for neurologic prognostication. EEG- electroencephalogram; SSEP- somatosensory evoked potential; MRI- magnetic resonance imaging.

4.14.a Computerized tomography of the brain- Loss of grey-white differentiation (gray-white ratio of Hounsfield Units <1.2) on initial CT of the brain predicts survival and neurologic outcome following cardiac arrest. [39-41] Subjects with a grey-white ratio <1.2 will be excluded from the study.

4.14.b Somatosensory evoked potentials- Subjects without a motor response to painful stimuli (GCS Motor=1) at 72 hours following cardiac arrest will have SSEP's obtained as part of the standard protocol. A lack of N20 response bilaterally remains predictive for a poor neurologic outcome following cardiac arrest. [42]

4.14.c Magnetic Resonance Imaging- Subjects who remain unconscious for >72 hours after cardiac arrest may receive MRI of the brain. Whole brain ADC mapping $<750 \times 10^{-6}$ mm²/sec has been associated with a mRS of >3 in prior work. [43]

4.14.d Neuronal Specific Enolase/S100B- These are not available clinically in our local facilities and have varying associations with neurologic outcome. [7, 42, 44]

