4.13 Daily Examinations

A study physician will complete a neurologic examination upon hospital arrival and again once the subject has rewarmed to a core temperature of $>36^{\circ}\text{C}$. [Table 4] The initial examination is used to determine the category of initial illness severity. [2] Daily examinations will not be performed until sedative medications have been discontinued for at least 40 minutes. [36] Our facility uses propofol for the majority of patients. In subjects receiving continuous infusion of midazolam, the midazolam will be discontinued for 60 minutes before examination. In the rare instance of neuromuscular blockade use, examinations will not be completed until the train of four monitor reads 4/4. Following rewarming, this examination will be completed daily. Prior literature has demonstrated that individual findings are less predictive for outcome in the modern era, thus, no one finding will result in cessation of support. [7, 37, 38]

[figure not shown]

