4.15 Statistical Analysis

4.15.a Random Assignment

Those eligible for the study will be randomly assigned with equal probability to the experimental condition (amantadine) or the control condition (placebo). Random assignment will be stratified by cardiac arrest category (PCAC) and presence of malignant EEG patterns (only in those with PCAC II), resulting in four strata: PCAC IV, PCAC III, PCAC II with malignant EEG patterns, and PCAC II without malignant EEG patterns. Survival markedly differs between these strata. [Section 3.C.1.b]

To maximize the probability of a balanced design, assignments will occur in block of two and four within each stratum. To ensure that the research team will be masked to the next treatment assignment, the size of the block will be randomly generated.

Random assignment will occur through the University of Pittsburgh Investigational Drug Service (IDS). Study staff will contact the IDS pharmacist, provide the necessary information (e.g., stratum) and the random assignment will be delivered. Given the volume of clinical studies at the University of Pittsburgh, IDS pharmacy medications and randomization are available 24/7.

4.15.b Data Analysis

The data analysis will begin by describing the baseline characteristics of the population. Summary statistics, such as means, standard deviations and frequencies will be generated. Graphical techniques, such as scatter plots and box plots will be used to evaluate the distribution of the baseline characteristics.

The balance of the baseline characteristics across treatment group will be compared. For discrete characteristics a chi-square tests or Fisher's exact test will be used to compare the proportions across treatment group. For continuous measures, either t-tests or Wilcoxon tests will be used to compare the characteristics across treatment group.

Aim 1, Hypothesis 1: Administration of amantadine after cardiac arrest will decrease time to awakening when compared to placebo during the 7 days of treatment.

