Kaplan-Meier curves will be generated for time-to-awakening for each treatment group and a log-rank statistic will be used to compare the cumulative probability of awakening across treatment groups. Those participants who are not awake by treatment day 7 will be considered censored observations. A Cox proportional hazards regression model will be used to compare time-to-awakening by treatment group controlling for baseline characteristics that are not balanced through random assignment and stratification variables. The assumptions of the Cox proportional hazards model will be evaluated (proportionality of the hazards model) and if violated, a split analysis will be conducted.

Aim 1, Hypothesis 2: A larger proportion of subjects will awaken during the first 7 days of treatment after administration of amantadine when compared to placebo.

A chi-square test will be used to compare the proportion of participants that are awake at day 7 between the two treatment groups. Logistic regression model will be used to compare the proportions by treatment group controlling for baseline characteristics that are not balanced through random assignment and stratification variables.

Aim 2: Determine if the number of serious adverse events differ between subjects randomized to amantadine and subjects randomized to placebo.

It is anticipated that given the severe critical state of those enrolled in the study, each study participant will have multiple serious adverse events. A t-test (or Wilcoxon test) will be used to compare the means number of serious adverse events that occurred during the 7 days after treatment initiation. A regression model will be used to compare the means after controlling for baseline characteristics that are not balanced through random assignment and stratification variables. The type of regression model will depend in the distribution of the number of serious adverse events and could be a linear regression model, negative binomial model, or Poisson model.

4.15.c Sample Size

The sample size calculations are based on the analysis approach for the primary hypothesis (Aim 1, Hypothesis 1) with a type I error rate of 0.05, a two-sided alternative hypothesis, and 80% power. Based on these assumptions, a sample of 120 (60 per treatment group) will be sufficient to detect a difference of awakening of 30% in the control group and 50% in the active treatment group.

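### The two posturing labels in the Table 4 motor item appear transposed, so scoring as written can misclassify initial severity in patients with posturing

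*Combined protocol and SAP*

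**What the plan says.** Table 4 in section 4.14 defines the clinical examination. Its motor item gives code 0 to an absent response (or myoclonus) and continues "1- Decorticate posturing 2- Decerebrate posturing or withdraw to pain 3- Localization 4- Following commands", with the instruction "The best motor response will be recorded".

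Section 4.13 refers to Table 4 for the examination at arrival and states: "The initial examination is used to determine the category of initial illness severity". The rule that turns findings into a category is cited to a reference and not reproduced. The same examination is repeated daily after rewarming.

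Section 4.15.a stratifies randomization on PCAC and, within PCAC II, on EEG, "resulting in four strata: PCAC IV, PCAC III, PCAC II with malignant EEG patterns, and PCAC II without malignant EEG patterns". In section 4.15.b the Cox, logistic and serious-adverse-event models compare the arms "controlling for baseline characteristics that are not balanced through random assignment and stratification variables".

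Section 4.14.b also uses the Glasgow Coma Scale motor score: "Subjects without a motor response to painful stimuli (GCS Motor=1) at 72 hours" have SSEPs obtained.

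**The concern.** The item is an ordered scale, from no response up to following commands, and an instruction to record the best response only works if a higher code means a better response. In the conventional order, extensor (decerebrate) posturing is worse than flexor (decorticate) posturing, which is worse than withdrawal. Table 4 puts decorticate posturing below decerebrate posturing and gives decerebrate posturing the same code as withdrawal.

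This is not a coarser grouping of neighbouring levels. Code 2 joins the levels on either side of decorticate posturing, and decorticate posturing itself gets the lower code 1. In a patient with decorticate posturing on one side and decerebrate on the other, taking the higher code as the best response records the worse sign. If only the code is stored, decerebrate posturing and withdrawal cannot be told apart later.

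What is at stake is the accuracy of the initial severity category, and through it the strata and the covariates.

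**Working it through.** The plan gives no figure to reproduce here. The check is one of order, followed by a trace of where the codes are used.

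**Step 1. Inputs.** The Table 4 codes are as printed. The conventional Glasgow motor order is an assumption, because the documents print only the value 1, for no response.

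| Response | Table 4 code | Conventional rank |
|---|---|---|
| None (or myoclonus) | 0 | 1 |
| Decerebrate | 2 | 2 |
| Decorticate | 1 | 3 |
| Withdrawal | 2 | 4 |
| Localization | 3 | 5 |
| Following commands | 4 | 6 |

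**Step 2. Pairwise order.** Six responses give 6 × 5 / 2 = 15 pairs. A pair is inverted if the code difference and the rank difference have opposite signs, and tied if the code difference is zero.

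- Decorticate against decerebrate: codes 1 − 2 = −1, ranks 3 − 2 = +1. Inverted.
- Decerebrate against withdrawal: codes 2 − 2 = 0, ranks 2 − 4 = −2. Tied across a skipped level.
- The other 15 − 2 = 13 pairs are in order.

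**Step 3. The same check with the labels exchanged** (decerebrate 1; decorticate or withdrawal 2). No pair is inverted. One pair is tied, decorticate with withdrawal, and these are adjacent (ranks 3 and 4). That one exchange restores the order is why the entry reads as a transposition.

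**Step 4. Where the codes are used.**

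| Use | What it needs | Depends on code 1 versus 2? |
|---|---|---|
| Awakening (4.1) | Code 4 | No |
| Exclusion on motor and SSEP findings (Table 2) | None versus any response | No |
| SSEP trigger (4.14.b) | None versus any response | No |
| PCAC category (4.13), strata (4.15.a), model covariate (4.15.b) | Rule not in the documents | Cannot be determined |

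**Step 5. Size.** The effect on the strata runs from none, if no PCAC boundary depends on code 1 versus code 2, to some patients with posturing being placed in the wrong category, if one does. The documents give no frequency of posturing at arrival. For illustration only, an assumed 5% to 15% of the 120 subjects would be 0.05 × 120 = 6 to 0.15 × 120 = 18 with a posturing code. That counts subjects exposed to the ambiguous codes, not subjects in a wrong stratum.

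**The case against.** The strongest reply is that nothing traceable in the plan depends on the difference between codes 1 and 2. The endpoint, the exclusion and the SSEP trigger do not use it, and no listed analysis uses the intermediate motor codes directly. Sections 4.13 and 4.14 also say that no single finding will lead to cessation of support. PCAC may be assigned from a separate score, or codes 1 and 2 may fall in the same category. The slip may be confined to the printed table. This is a single-center trial in which a study physician does the examination, so practice may already follow the usual order. Thirteen of 15 pairs are correct. All of this stands, and it limits the consequence.

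It does not remove the defect. Table 4 is the only scoring definition the plan gives for an examination that sets the severity category, and with the PCAC rule absent a reader cannot confirm that the error is harmless.

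A reader might infer that patients are in fact being randomized in the wrong stratum. The documents do not support that, because they give no PCAC cut-point. Nor do they support the inference that the treatment comparison is biased. The category comes from the examination at arrival, before allocation, so any error is unrelated to arm.

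**Conclusion.** The labelling anomaly holds: one inverted pair and one non-adjacent tie, given the conventional motor order. Scoring as written can misclassify initial severity in patients with posturing. Whether any patient changes PCAC stratum is undetermined.

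At worst, the strata and the covariate adjustment would carry some noise, with some loss of balance and precision. The randomized comparison remains valid and the awakening endpoint is untouched. Severity is minor to moderate; this is not a defect that must be resolved before the trial can be interpreted. The conclusion rests on two assumptions: that the conventional order is the one intended, and that the case report form follows the printed table, which cannot be seen from the documents.

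**What to change.** 1. Check the motor item in Table 4 and on the case report form against the source scale. Correct the order so that code 1 is decerebrate posturing and code 2 is decorticate posturing or withdrawal to pain; codes 0, 3 and 4 stay as they are.
2. Record the named sign alongside the code. The corrected code 2 still pools two signs, so only this step allows them to be separated later.
3. State in the plan the rule that maps examination findings to PCAC II, III and IV, so that its dependence on the motor code can be seen.
4. Recheck the PCAC of any subject already coded 1 or 2.

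The cost is one line in the table and on the form, one added field, a short statement of the PCAC rule and a short chart check. No extra assessment of subjects is needed.

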4.15 Statistical Analysis

4.15.a Random Assignment

Those eligible for the study will be randomly assigned with equal probability to the experimental condition (amantadine) or the control condition (placebo). Random assignment will be stratified by cardiac arrest category (PCAC) and presence of malignant EEG patterns (only in those with PCAC II), resulting in four strata: PCAC IV, PCAC III, PCAC II with malignant EEG patterns, and PCAC II without malignant EEG patterns. Survival markedly differs between these strata. [Section 3.C.1.b]

To maximize the probability of a balanced design, assignments will occur in block of two and four within each stratum. To ensure that the research team will be masked to the next treatment assignment, the size of the block will be randomly generated.

Random assignment will occur through the University of Pittsburgh Investigational Drug Service (IDS). Study staff will contact the IDS pharmacist, provide the necessary information (e.g., stratum) and the random assignment will be delivered. Given the volume of clinical studies at the University of Pittsburgh, IDS pharmacy medications and randomization are available 24/7.

4.15.b Data Analysis

The data analysis will begin by describing the baseline characteristics of the population. Summary statistics, such as means, standard deviations and frequencies will be generated. Graphical techniques, such as scatter plots and box plots will be used to evaluate the distribution of the baseline characteristics.

The balance of the baseline characteristics across treatment group will be compared. For discrete characteristics a chi-square tests or Fisher's exact test will be used to compare the proportions across treatment group. For continuous measures, either t-tests or Wilcoxon tests will be used to compare the characteristics across treatment group.

Aim 1, Hypothesis 1: Administration of amantadine after cardiac arrest will decrease time to awakening when compared to placebo during the 7 days of treatment.

Kaplan-Meier curves will be generated for time-to-awakening for each treatment group and a log-rank statistic will be used to compare the cumulative probability of awakening across treatment groups. Those participants who are not awake by treatment day 7 will be considered censored observations. A Cox proportional hazards regression model will be used to compare time-to-awakening by treatment group controlling for baseline characteristics that are not balanced through random assignment and stratification variables. The assumptions of the Cox proportional hazards model will be evaluated (proportionality of the hazards model) and if violated, a split analysis will be conducted.

Aim 1, Hypothesis 2: A larger proportion of subjects will awaken during the first 7 days of treatment after administration of amantadine when compared to placebo.

A chi-square test will be used to compare the proportion of participants that are awake at day 7 between the two treatment groups. Logistic regression model will be used to compare the proportions by treatment group controlling for baseline characteristics that are not balanced through random assignment and stratification variables.

Aim 2: Determine if the number of serious adverse events differ between subjects randomized to amantadine and subjects randomized to placebo.

It is anticipated that given the severe critical state of those enrolled in the study, each study participant will have multiple serious adverse events. A t-test (or Wilcoxon test) will be used to compare the means number of serious adverse events that occurred during the 7 days after treatment initiation. A regression model will be used to compare the means after controlling for baseline characteristics that are not balanced through random assignment and stratification variables. The type of regression model will depend in the distribution of the number of serious adverse events and could be a linear regression model, negative binomial model, or Poisson model.

4.15.c Sample Size

The sample size calculations are based on the analysis approach for the primary hypothesis (Aim 1, Hypothesis 1) with a type I error rate of 0.05, a two-sided alternative hypothesis, and 80% power. Based on these assumptions, a sample of 120 (60 per treatment group) will be sufficient to detect a difference of awakening of 30% in the control group and 50% in the active treatment group.

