4.4 Randomization

After informed consent, subjects will be randomly assigned to either amantadine or placebo. For intention-to-treat analysis, subjects will be considered to be randomized as soon as an assignment is made. For per-protocol analyses, subjects will be considered to be randomized after receiving the first dose of study medication. The Investigational Drug Service (IDS) at the University of Pittsburgh will prepare and

dispense study drug and maintain the block randomization list. At randomization, subjects will be stratified by PCAC strata and presence of early malignant patterns on EEG recording (these EEG patterns must have stopped by time of randomization, because continued malignant EEG is an exclusion). Both of these have been associated with outcome. [2, 16, 32, 3.C.1.b]

Table 2. Inclusion and Exclusion Criteria

Inclusion Criteria	Exclusion Criteria
Non-traumatic cardiac arrest	Written do not attempt resuscitation (DNAR) reported to providers before randomization
Age 18 years or more	Known prisoner or pregnancy
Defibrillation and/or chest compressions by healthcare providers	Lack of motor response to pain and absent N2O response on SSEP prior to randomization.
Return of spontaneous circulation	Initial CT demonstrating brain edema (defined as grey white ratio <1.2)
	Presence of malignant pattern on EEG at time of randomization.
	Next of kin unwilling to provide supportive care for at least one week after enrollment.
	Creatinine clearance <50mL/min
	Presently using other dopaminergic agent

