4.11 EEG Protocol

We obtain a 22-channel digital EEG with simultaneous video recording on all patients resuscitated from cardiac arrest in our facility. This permits correlation of motor activity with electrographic findings and allows for accurate diagnosis of malignant EEG patterns. Contemporaneous interpretation is provided by the Department of Neurology. Subjects will be classified as demonstrating a malignant pattern or not using standard definitions. **[Table 3]** Locally, the PCAC II illness severity phenotype with malignant EEG patterns has a markedly reduced survival when compared to PCAC II illness severity without malignant EEG patterns.

Thus, subjects will be stratified on PCAC and (in the PCAC II illness severity subjects) presence of malignant EEG pattern prior to randomization. If malignant patterns do develop, we will provide therapy to suppress the EEG and any clinical evidence of seizures. **[Figure 3]** This ensures a standard approach to all subjects in the study. Importantly, subjects with malignant EEG patterns that persist beyond 48 hours are excluded from the study and will not be enrolled.

Figure 3. Standardized antiepileptic treatment algorithm for malignant EEG patterns. (Malignant= GPED's, MSE, NCSE)

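### The tests listed first for Hypotheses 1 and 2 ignore the randomization strata, and the adjusted models choose their extra covariates by observed imbalance rather than by prognostic value

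*Combined protocol and SAP*

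**What the plan says.** Section 4.15.a assigns patients 1:1 in random blocks of two and four within four strata: PCAC IV, PCAC III, PCAC II with malignant EEG and PCAC II without. It gives the reason: "Survival markedly differs between these strata". Section 4.11 describes the same scheme ("subjects will be stratified on PCAC and (in the PCAC II illness severity subjects) presence of malignant EEG pattern prior to randomization"). Section 4.4 names the same two factors without stating that the EEG split applies only to PCAC II ("subjects will be stratified by PCAC strata and presence of early malignant patterns on EEG recording").

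Section 4.15.b then lists two analyses for each Aim 1 hypothesis:

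- Hypothesis 1 (time to awakening): "a log-rank statistic will be used to compare the cumulative probability of awakening across treatment groups", followed by a Cox model.
- Hypothesis 2 (awake at day 7): "A chi-square test will be used to compare the proportion of participants that are awake at day 7 between the two treatment groups", followed by a logistic model.

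Neither the log-rank nor the chi-square is described as stratified. Both models are to be fitted "controlling for baseline characteristics that are not balanced through random assignment and stratification variables". The arms are first compared at baseline ("The balance of the baseline characteristics across treatment group will be compared"), by chi-square or Fisher's exact test for discrete variables; for continuous ones, "either t-tests or Wilcoxon tests will be used to compare the characteristics across treatment group". The section gives no candidate covariates and no threshold for imbalance. It does not say whether the test or the model decides a hypothesis. Section 4.15.c refers only to the analysis approach for Hypothesis 1, which contains both.

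**The concern.** There are two separate issues.

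**Strata.** Blocking within strata makes the arms nearly equal in stratum mix. If the strata predict awakening, the difference between arms then varies less than an unstratified test assumes. The test uses too large a variance, rejects too rarely under the null and loses power. The strata were chosen because they are prognostic, so a test that ignores them gives away part of what the design provides.

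**Covariates.** Adjustment gains power when a covariate predicts the outcome. Imbalance between randomized arms is chance and carries no information about prediction. A rule that admits covariates by imbalance will usually omit a strong predictor, and the form of the adjusted model is unknown until the baseline data are seen.

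**Working it through.** **The plan's own figure.** Section 4.15.c states 80% power for 30% v 50% awakening with 120 patients, two-sided 5%.

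- Under proportional hazards, HR = ln(1 − 0.50)/ln(1 − 0.30) = 1.943.
- Expected events = 60 × 0.30 + 60 × 0.50 = 48.
- Log-rank power = Φ(√(48/4) × ln 1.943 − 1.96) = Φ(0.34) = 63%.

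The stated 80% is not reproduced. That is a separate sample-size matter. It is noted here because it explains why the simulated powers below start near 0.62. Only differences between methods are used.

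**Strata: assumptions.** The documents give no stratum shares or awakening rates, so these are assumed. The order is PCAC II without malignant EEG, PCAC II with, PCAC III, PCAC IV.

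- Shares: 35/15/20/30%.
- Control awakening: none 30/30/30/30%, mild 38/25/30/22%, moderate 46/21/31/15%, strong 60/10/25/8%, scaled to average 30%.
- Within-stratum HR, solved for a treated average of 50%: 1.94, 1.97, 2.05, 2.40.

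**Why the unstratified test is conservative.** Under the null with strata balanced by blocking, the chi-square's z statistic has variance of about Σwₛpₛ(1 − pₛ) / [p̄(1 − p̄)].

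- Moderate (unscaled rates): 0.1929/0.2098 = 0.919, SD 0.959. The nominal cut-off of 1.96 acts as 1.96/0.959 = 2.04, so null rejection is about 4.1%.
- Strong: 0.1571/0.2096 = 0.749, SD 0.866. The cut-off acts as 2.26, so null rejection is about 2.4%.

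**Strata: simulation.** 10,000 trials per scenario, N = 120, blocks of 2 and 4 within strata, exponential awakening times censored at day 7, death and withdrawal of care not simulated. Simulation error is about 0.5 points for power and 0.2 for null rejection.

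| | None | Mild | Moderate | Strong |
|---|---|---|---|---|
| Power, log-rank | 0.629 | 0.623 | 0.645 | 0.673 |
| Power, stratified log-rank | 0.623 | 0.633 | 0.692 | 0.847 |
| Power, Cox with strata | 0.627 | 0.634 | 0.694 | 0.849 |
| Power, chi-square | 0.623 | 0.616 | 0.634 | 0.639 |
| Power, Cochran-Mantel-Haenszel | 0.622 | 0.622 | 0.670 | 0.775 |
| Power, logistic with strata | 0.626 | 0.626 | 0.675 | 0.774 |
| Null rejection, log-rank | 0.047 | 0.053 | 0.040 | 0.025 |
| Null rejection, chi-square | 0.047 | 0.055 | 0.039 | 0.025 |

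Gain from stratifying, in points: log-rank −0.6, 1.0, 4.7, 17.4; chi-square −0.1, 0.6, 3.6, 13.6. The models with strata match the stratified tests within 1 point.

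A different set of assumed rates (2,000 runs) gives a similar picture for the log-rank. Power is 0.55 unstratified v 0.57 stratified with mild strata, and 0.39 v 0.54 with strong strata, where unstratified null rejection is 2.3%.

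**Covariates: assumptions and simulation.** 5,000 trials per setting, moderate strata, Cox with strata, 10 independent standard normal covariates of which one is prognostic, balance test at 5%. The number of covariates, the HRs and the threshold are assumed.

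| HR per SD of the predictor | 1.0 | 1.5 | 2.0 |
|---|---|---|---|
| Power, strata only | 0.689 | 0.693 | 0.678 |
| Power, plus covariates with balance p < 0.05 | 0.685 | 0.686 | 0.676 |
| Power, plus pre-specified predictor | 0.689 | 0.727 | 0.769 |

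The balance test selected the predictor in about 5% of trials in every setting, as randomization implies. The loss against pre-specification is 0.727 − 0.686 = 4.1 points and 0.769 − 0.676 = 9.3 points. A repeat run gave 0.65 v 0.71 and 0.68 v 0.78, so 6 and 10 points. Simulation error in the tabulated powers is about 0.7 points.

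**The case against.** The strongest reply is that the plan already deals with the strata. On its natural reading the covariate sentence puts the stratification variables into both models. It can also be parsed as characteristics left unbalanced by randomization and stratification, but that reading is strained. So the power loss arises only if the simple test decides. This stands, and it limits the first issue to that case.

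The sizes are also open to challenge. The plan's remark on strata concerns survival, not awakening. The exclusions in Table 2 (ongoing malignant EEG, early brain edema, absent motor response with absent SSEP response) may narrow stratum differences. The simulation leaves out withdrawal of care, which section 4.12 links mainly to persistent coma. The 5% balance threshold is not in the plan. The covariate loss is measured against a predictor known in advance; against strata alone, imbalance-based selection costs under 1 point (0.693 v 0.686; 0.678 v 0.676). All of this stands, and the figures are illustrative.

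A reader might infer three stronger things that the documents do not support:

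- *The unstratified tests are invalid.* They are not; any error is on the conservative side.
- *Leaving the deciding analysis unnamed inflates false positives.* Counting success if either the log-rank or the Cox model is significant gives null rejection of 5.0–5.8%, so the effect is small. The choices between chi-square and Fisher, or t-test and Wilcoxon, are ordinary missing detail.
- *Covariate selection materially inflates false positives.* Null rejection reaches about 6–7% only if the model is run without covariates and at 5%, 10% and 20% thresholds and any success counts. The plan proposes no such thing, and each version alone gives 4.4–5.2%.

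**Conclusion.** The point holds as a matter of efficiency and pre-specification. It does not threaten validity.

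The tests listed first do not use strata that the plan itself regards as prognostic. If they decide, the expected loss is about 0 to 5 points of power for none-to-moderate separation. The 14 to 17 points need control awakening of roughly 60% in one stratum and 8–10% in others, which nothing in the documents establishes, so that figure should not drive the grading.

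The models avoid this loss but choose their remaining covariates by a criterion unrelated to prognosis. The cost is about 4 to 10 points against pre-specifying a real predictor with an HR of 1.5 to 2.0 per SD, and none if no covariate is prognostic.

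With about 48 events expected at the plan's rates, a free gain is worth taking. It should be changed; confidence in the size is moderate because every stratum rate, covariate effect and threshold is assumed.

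**What to change.** In section 4.15.b, before unblinding:

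- **Deciding analysis.** Name one per hypothesis that uses the four strata listed in section 4.15.a. For Hypothesis 1, use a stratified log-rank with a stratified Cox hazard ratio, or the planned Cox model with stratum terms. For Hypothesis 2, use Cochran-Mantel-Haenszel, or the planned logistic model with stratum terms.
- **Stratum.** Reword the covariate sentence so that the stratum is always included. Align section 4.4 with sections 4.11 and 4.15.a on where the EEG split applies, so that the analysis stratum is the one used for randomization.
- **Covariates.** Replace selection by imbalance with a short list of prognostic covariates fixed in advance, or with none. Baseline comparisons can remain as description.
- **Sensitivity.** Keep the unstratified log-rank and chi-square as sensitivity analyses.

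This applies whichever hypothesis is primary. The cost is SAP wording only. The one small downside is that a very small stratum contributes little information to a stratified analysis.
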